RESEARCH PROTOCOL

Study identification data

Study Title

Conservative approach to dysfunctional pain in women

Study version number and date

V.01 (01-12-2021)

Promoter and direction

[name]. [name]

Principal Investigator and Director

[name]. [name]

Service or Unit

Gynecology/Rehabilitation

Centers where the study is planned (multicenter studies)

Hospitals of Sagunto, La Plana, IMSKE Valencia and University of Valencia

Study Summary

Study that will seek to compare the effects of the implementation of a therapeutic education program in women suffering from dyspareunia for a period of more than three months who do not have any previous medical condition that can logically explain this condition. The effects of three groups will be compared; one that attends face-to-face workshops, another that will receive access to a website where the educational content will be, and a third that will serve as control.

Study Introduction

This research project is entitled "Conservative approach to the patient with dysfunctional pain in the pelvic floor in women". It will be carried out both by researchers from the University of Valencia and by external researchers from other hospitals.

Conservative approach to dysfunctional pain in women

We understand dysfunctional pain as pain that stops fulfilling the function of "alarm signal" and that stops responding to a nociceptive stimulus (1). This alarm signal can be triggered by previous pathologies, such as endometriosis (2) or musculoskeletal conditions such as muscle hypertonia (3) or neuralgia (4).

Despite this, this pain can also originate without the existence of any of the previous conditions, therefore without having a clear origin that can be addressed through treatment. In the pelvic floor, this dysfunctional pain can come to take different names, among which we highlight "dyspareunia" and "vestibulodynia" (5).

"Dyspareunia" is a term derived from the Greek that means lovers who do not fit together (6), and it is a sexual disorder that is defined by the presence of pain and discomfort during the sexual act, in addition to being predominantly associated with the attempt or achievement of sexual intercourse. complete vaginal penetration (7). Prevalence levels range from 3% to 43%, and vary depending on different cultures and settings (6) (8).

Study justification

The lack of a good educational level in women's health disorders can lead to misinterpretations about normality, and these end up causing both sexual and emotional repercussions (8). It is a common misconception that intercourse can sometimes be painful, and many women are forced to continue intercourse even in pain, even having to clench their teeth.

Because of this, women who suffer from dysfunctional pelvic floor pain develop clinically relevant comorbidities, especially psychological ones, such as depression, anxiety or erotophobia (6) (8) .

Conservative approach to dysfunctional pain in women

For this reason, the treatment of dysfunctional pain with therapeutic educational sessions is proposed so that women who suffer from dyspareunia are able to better understand the processes of this condition and, possibly, solve it.

Study Objectives

The main objective of this study is to compare the effects of implementing a therapeutic educational program on pelvic floor pain and dysfunction in patients with dysfunctional pain. This program will be administered both in person at workshops organized in different centers, and online through a web platform.

As a secondary objective, the adherence levels of each of the proposed educational programs will be analyzed.

Material and methods

Design

Randomized controlled clinical trial.

Disease or Study population and total number of subjects

Women with dysfunctional pelvic floor pain that cannot be explained by another underlying medical cause

Selection criteria (inclusion and exclusion)

Women who (1) are of legal age, (2) have suffered from dyspareunia for more than 3 months and (3) do not have any medical condition that logically explains the presence of pain

Main variables

Level or intensity of pain, evaluated using subjective perception scales (Visual Analogue Scale or VAS).

Conservative approach to dysfunctional pain in women

Secondary variables

Other questionnaires related to dysfunctional pain; Pain Catastrophizing Scale to quantify the patient's individual experience of pain, the Multidimensional Pain Inventory to measure the impact of pain on the patient's life, the Survey of Pain Attitudes related to the patient's beliefs about pain, and the Female Sexual Function Index related to the patient's sexual function.

The levels of adherence to the different programs will also be evaluated, established by the percentage of sessions completed based on the total number of sessions offered.

Interventions/procedures to be performed

Initial phase of patient recruitment from various hospital centers and by broadcasting with an informative video on RRSS through the official profiles on Instagram, Facebook and Twitter of the University of Valencia and the Illustrious College of Physiotherapists of the Valencian Community. The hospital centers that will initially be considered for obtaining the sample are the La Plana and Sagunto Hospitals and the IMSKE Hospital in Valencia. After this first phase, and using the established inclusion and exclusion criteria, randomization of all the participants into three different groups. The randomization method will be a simple randomization performed through computer software.

One group (1) will receive a therapeutic education program on pelvic floor pain and dysfunction in person as workshops held at collaborating centers, a second group (2) will receive access to a web platform where they can view as online content this same educational program and a third group (3) that will serve as control.

Conservative approach to dysfunctional pain in women

Both group (1) and group (2) will receive the same educational content, the only thing that will change is the modality in which they can access it, face-to-face through workshops given by specialist trainers, or access to an online platform where the contents previously recorded by these same trainers will be.

a "forum" will be opened on the same website where they can comment on their doubts). Each workshop will last approximately one hour, and the schedule will be established according to the possibilities of the participants.

The web platform will be developed thanks to a researcher who already has an online studio where she teaches therapeutic exercise classes, available at <[name]>. Participants who have been randomized in the online group will be given an access code to be able to enter the online space where they will have both the audiovisual material that has been previously developed by the researchers and a forum where they can discuss their doubts.

Regarding the control group, initially the participants of this group will not receive any of the two previous interventions, this group will serve to establish how the condition is maintained without a therapeutic approach. Once the intervention has finished and the post measurements have been collected, the participants of this group will also be given access to the online study so that they can view the contents and comment through the forum.

Work calendar

Calendar	Exercise	Place	Responsible
October to December 2021	Subject Selection	H. La Plana, H. IMSKE, H. Sagunto, University of Valencia	[name], [name], [name]
December 2021 to January 2022	Measurements prior to the start	H. La Plana, H. IMSKE, H. Sagunto,	[name], [name]

Conservative approach to dysfunctional pain in women

	of the intervention	University of Valencia	[name], [name]
January to March 2022	Intervention. Educational sessions on dysfunctional pain	H. La Plana, H. IMSKE, H. Sagunto, University of Valencia and online modality	[name], [name], [name]
March to April 2022	Post-intervention measurements	H. La Plana, H. IMSKE, H. Sagunto, University of Valencia and online modality	[name], [name], [name]
April 2022	Preparation of a scientific article with the results obtained from the research		[name]

Statistical analysis of data: equal to or less than 0.05)

The study design aims to collect pre and post measurements with various interventions. To do this, since these are pre and post measurements with several groups, a factorial ANOVA will be carried out, a repeated measurement factor (time) and a factor between groups (intervention).

The changes that are intended to be achieved are, with respect to the main variable, a significant reduction in the values of the VAS scale that corresponds to an improvement in terms of pain intensity. Regarding the secondary variables, significant changes in the score of the questionnaires on dysfunctional pain and sexual function that indicate clinical improvements regarding the impact of pain on the life

Conservative approach to dysfunctional pain in women

of the participant and the beliefs about the pain of the same, and on the levels of adherence, find high values to be able to relate the results obtained with the implementation of the program.

Sample size calculation and sampling procedure

The sample size was determined using the G-Power computer program. An a priori size calculation was performed with an effect power of 80% and an alpha error of 0.05. It was determined that the sample must have a minimum of 48 participants, and that each group must have a minimum of 16. Taking into account possible drop-outs, it was determined that a minimum sample of 60 participants and 20 participants for each group.

Ethical aspects and data confidentiality

This research deals with the implementation of an educational program on dysfunctional pelvic floor pain in women. It does not involve an invasive or aggressive intervention that could cause negative effects on the participants. In addition, if the final result is positive, there will be a tool that is easy to implement daily for the treatment of patients with this problem.

Conservative approach to dysfunctional pain in women

The subjects will be informed at all times of how the research will proceed, and before being included in the study sample they will be required to give their consent, both verbal and written, to participate in this research.

We will ensure that the data provided by patients is strictly confidential. Patients will be coded to ensure their anonymity and both the principal investigator and the person in charge of processing the statistical data will be blinded to the group assignment and to which patient corresponds to which value.

During the development of the investigation there will be no interference with regard to medical action. Once the study is over, and if the result is positive, the medical staff will be provided with the material with which the research has been carried out so that they can use it in their daily practice.

Sources of funding

The study has sufficient material and human resources to carry it out. Two researchers will coordinate its development, and the rest of the researchers will be in charge of carrying out the measurements prior to the start of the intervention, implementing the educational program and finally performing the measurements again. No medication will be supplied and there is no need for funding to carry out this research.

Bibliography

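### Simple randomisation does not secure the plan's group sizes: with 60 women, some arm starts below the stated minimum of 16 in 31.7% of trials

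*Combined protocol and SAP*

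**What the plan says.** Under *Sample size calculation and sampling procedure*, the protocol sets a floor for each group: "It was determined that the sample must have a minimum of 48 participants, and that each group must have a minimum of 16". The basis given is: "An a priori size calculation was performed with an effect power of 80% and an alpha error of 0.05". After an allowance for drop-out, the entry target becomes "a minimum sample of 60 participants and 20 participants for each group".

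Under *Interventions/procedures to be performed*, women are first recruited. Then comes "randomization of all the participants into three different groups", and the method is given in one line: "The randomization method will be a simple randomization performed through computer software". No blocks, strata, cap per arm or other balancing rule is described, and neither section refers to the other.

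The analysis, under *Statistical analysis of data*, is a mixed ANOVA: "a factorial ANOVA will be carried out, a repeated measurement factor (time) and a factor between groups (intervention").

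**The concern.** Simple randomisation, in its standard meaning, assigns each woman independently. The three arm sizes are then random and only their sum is fixed. The sample size section treats 20 per group at entry, and at least 16, as things the trial will have.

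The allowance of four women per arm (20 − 16) is there to absorb drop-out. Chance imbalance at allocation can use it up before the first workshop. The sponsor could recruit all 60 women and still miss its own floor in one arm. In a three-arm trial, every comparison that uses the small arm is then weaker than planned.

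**Working it through.** **Inputs from the protocol.** Three arms; 60 women at entry, 20 per group (so 1:1:1); floor of 16 per group, 48 in total; 80% power; alpha 0.05. Effect size, SD, pre-post correlation and drop-out rate are not stated.

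**The plan's own figures.** The step from 48 to 60 is reproduced by a 20% drop-out rate: 48/(1 − 0.20) = 60 and 16/0.80 = 20. The 48 has no unique derivation without an effect size. For example, 80% power at N = 48 needs f = 0.23 for the group × time interaction in a repeated-measures calculation with an assumed correlation of 0.5, or f = 0.46 for a one-way ANOVA.

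**Step 1: arm sizes at entry.** Under simple randomisation the sizes follow a multinomial distribution:

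P(a, b, c) = 60! / (a! b! c!) × (1/3)^60, with a + b + c = 60.

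- P(20/20/20) = 60!/(20!)³/3^60 = 0.0136, or 1.4%. Some arm is below 20 in the other 98.6%.
- For one given arm, P(Binomial(60, 1/3) ≤ 15) = 10.7%.
- Summing P over all splits with every arm at 16 or more gives 68.3%, so P(some arm < 16) = 31.7%. A simulation of 1,000,000 trials gives the same figure.
- The smallest arm averages 16.3 and is 12 or fewer in 5.1% of trials.

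Sixty is a stated minimum. The same sum for larger totals:

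| N at entry | P(some arm < 16) |
|---|---|
| 60 | 31.7% |
| 66 | 12.5% |
| 72 | 4.3% |

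**Step 2: completers.** With independent drop-out at rate d, P(all arms keep ≥ 16) = Σ P(a, b, c) × Π P(Binomial(nᵢ, 1 − d) ≥ 16). For a fixed start of 20/20/20 it is P(Binomial(20, 1 − d) ≥ 16)³; at d = 0.20 this is 0.630³ = 0.25.

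| Drop-out | Simple | Fixed 20/20/20 |
|---|---|---|
| 5% (assumed) | 52% | 99% |
| 10% (assumed) | 34% | 88% |
| 15% (assumed) | 17% | 57% |
| 20% (implied by 48/60) | 6.5% | 25% |

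**Step 3: power.** With two time points, the group × time test is a one-way F-test on the pre-post change, with 2 and N − 3 df and noncentrality Σ nᵢ(μᵢ − μ̄)²/σ², where μ̄ is the mean weighted by group size. The effect is scaled to give 80% at 16/16/16 (f = 0.463 on the change score, assumed). Two patterns of mean change were tried, 1/1/0 and 1/0.5/0. Results are exact with no drop-out and come from 100,000 simulated trials with drop-out.

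| Drop-out | Mean power, simple | Mean power, fixed | Power < 80%, simple | Power < 80%, fixed |
|---|---|---|---|---|
| None | 88.0% | 88.9% | 2–3% | 0% |
| 10% | 83.8% | 84.8% | about 17% | about 3% |
| 20% | 78.5% | about 79.5% | about 52–57% | about 47–52% |

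Ranges cover the two patterns. A single illustration with pattern 1/1/0: power is 0.89 at 20/20/20 and 0.83 at 23/22/15 when control is the arm of 15.

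**The case against.** The strongest reply is that 31.7% counts a mostly harmless event. A trial with one arm below 16 still has 60 women, and the larger arms largely make up for the small one. Under the Step 3 model with no drop-out, mean power among those trials is still 87%. Of the 31.7 percentage points, 28.3 to 29.8 are splits with power of 80% or more. At the one drop-out rate the documents imply, 20%, equal allocation changes the chance of falling below 80% power only from about 52–57% to about 47–52%. Equal allocation itself keeps 16 completers in every arm in only 25% of trials at that rate. All of this is correct. It means that 31.7% must not be read as the risk of an underpowered trial, and that the drop-out allowance is a separate weakness.

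A second reply is that the protocol may use the word simple loosely, for an equal split of one finished list by software. That would be compatible with 20 per group and would reduce the 31.7% to zero. Nothing in the text says it, however, and if it was meant, the same sentence still needs changing.

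Third, simple randomisation is valid and unbiased. That is agreed: neither bias nor an inflated type I error is at issue. What stands is that the protocol states group sizes as requirements and names a method that does not meet them, when a method that does is available at almost no cost.

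**Conclusion.** The concern holds. The randomisation and sample size sections do not fit together: simple randomisation of 60 women puts at least one arm below the stated floor of 16 in 31.7% of trials and gives the stated 20/20/20 in 1.4%. The consequence is modest. Mean power for the overall test falls by about 1 percentage point. The spread of power widens most at moderate drop-out, with power below 80% in about 17% against 3% of trials at an assumed 10%.

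The entry figures are exact for independent 1:1:1 assignment of exactly 60 women and fall as the total rises. The completer and power figures also rest on independent drop-out at the rates shown, and the power figures on an effect scaled to the plan's 80% at 16 per group. This should be fixed, but it does not threaten the trial's validity.

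**What to change.** Under *Interventions/procedures to be performed*, replace the simple randomisation sentence with:

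> After recruitment closes, participants will be allocated by one computer-generated random permutation of a list with equal numbers for the three groups (20/20/20 for 60 women; for other totals, group sizes differ by at most one).

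The chance that an arm starts below 16 with 60 women falls from 31.7% to zero. The cost is one sentence and a different option in the same software. No extra participants or visits are needed and the planned ANOVA is unchanged. The protocol already has all women randomised together after the recruitment phase, and its calendar puts selection (October to December 2021) before the intervention (January 2022). A single list drawn at that point therefore leaves no later enrolment decision that could be influenced by predicting the next allocation.

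This change settles group sizes at entry only. Whether 20 per group leaves enough room for drop-out has to be dealt with separately.

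### The planned time-by-intervention ANOVA on VAS is a change-score test; ANCOVA on the baseline VAS already being collected is valid too and usually more powerful

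*Combined protocol and SAP*

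**What the plan says.** The main variable is pain on a VAS (Main variables): "Level or intensity of pain, evaluated using subjective perception scales (Visual Analogue Scale or VAS". Two measurement occasions are planned (Statistical analysis of data): "The study design aims to collect pre and post measurements with various interventions". The Work calendar schedules the first of these before the intervention begins, so every randomised woman should have a baseline VAS.

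The analysis is described in the same statistical section: "a factorial ANOVA will be carried out, a repeated measurement factor (time) and a factor between groups (intervention". The available text mentions no covariate, baseline adjustment or ANCOVA, and it does not say which term of the ANOVA is the treatment test.

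Two other statements bear on the point. Allocation is unrestricted (Interventions/procedures to be performed): "The randomization method will be a simple randomization performed through computer software". The trial is sized at a minimum (Sample size calculation and sampling procedure): "An a priori size calculation was performed with an effect power of 80% and an alpha error of 0.05", and "It was determined that the sample must have a minimum of 48 participants, and that each group must have a minimum of 16". Recruitment is raised to 60, 20 per arm, to cover drop-outs.

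**The concern.** A repeated-measures ANOVA with a single pre and a single post value uses the baseline only by subtracting it, that is, with its slope fixed at 1. ANCOVA estimates the slope from the data. Unless the true slope is close to 1, subtraction leaves avoidable noise in the comparison.

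Precision is scarce here. The 48 evaluable women are the minimum for 80% power, and the increase to 60 is set aside for drop-outs. Arms are small and simple randomisation does not restrict baseline differences between them, so the arms may well start at visibly different pain levels. When they do, the change score carries part of that difference into the estimated effect, usually by over-correcting (regression to the mean). At stake is the chance of detecting a real effect with the women recruited, not the type I error rate.

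**Working it through.** **Inputs from the documents.** Three arms, 16 evaluable per arm (48 in total), alpha 0.05, power 80%, one pre and one post VAS.

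**Inputs not in the documents.** The effect size, the SDs, the pre-post correlation rho and the G-Power test family. Rho is varied from 0.3 to 0.9, and k = SD_post/SD_pre from 0.8 to 1.4.

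**1. The plan's own figure.** N = 48 cannot be reproduced uniquely without the effect size. For the interaction test with f = 0.25, the requirement is 60, 51, 42 or 36 women at rho 0.3, 0.4, 0.5 or 0.6. N = 48 corresponds to f of about 0.23 at rho 0.5. Other routes also reach 48, for example a two-group comparison with a standardised difference of 1.0 (16 per arm). The step to 60 matches 48/(1 − 0.20) = 60. What follows takes the 80% at N = 48 as given for the planned interaction test.

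**2. Equivalence.** On one simulated data set, the time-by-group interaction F was 5.7504 and the one-way ANOVA F on change scores was 5.7504.

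**3. Validity.** Simulated type I error at rho 0.3, 0.5 and 0.7 was 0.047, 0.047 and 0.056 for the change score, and 0.047, 0.046 and 0.053 for ANCOVA. Both hold the 5% level to within simulation error.

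**4. Variance per woman (large samples).**
- Change score: SD_pre² + SD_post² − 2·rho·SD_pre·SD_post
- ANCOVA: SD_post²·(1 − rho²)
- Difference: (SD_pre − rho·SD_post)², which is never negative and is zero only when rho = SD_pre/SD_post
- Ratio, ANCOVA to change: k²(1 − rho²)/(1 + k² − 2·rho·k), which is (1 + rho)/2 when k = 1

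| k | rho 0.3 | rho 0.5 | rho 0.7 | rho 0.9 |
|---|---|---|---|---|
| 0.8 | 0.50 | 0.57 | 0.63 | 0.61 |
| 1.0 | 0.65 | 0.75 | 0.85 | 0.95 |
| 1.2 | 0.76 | 0.87 | 0.97 | 0.98 |
| 1.4 | 0.84 | 0.94 | 1.00 | 0.85 |

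**5. Power.** For F(2, 45) at alpha 0.05, 80% power needs a noncentrality of 10.31. Dividing by the ratio and using F(2, 44) gives ANCOVA power; at k = 1 and rho 0.5, 10.31/0.75 = 13.75, giving 90.4%. Simulation with the slope estimated (16 per arm, two active arms with equal effect, 40,000 trials per cell) gave:

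| k | rho 0.3 | rho 0.5 | rho 0.7 | rho 0.9 |
|---|---|---|---|---|
| 0.8 | 98% | 96% | 94% | 95% |
| 1.0 | 94% | 90% | 86% | 81% |
| 1.2 | 89% | 85% | 81% | 80% |
| 1.4 | 86% | 81% | 79% | 86% |

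The change-score test stood at 80% in every cell.

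**6. Sample size equivalent.** With equal SDs and rho 0.5, the noncentral F calculation reaches 80% for ANCOVA at 37 women, or 39 in three equal arms. Simulation gave about 81% with 39.

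**7. Baseline imbalance.** The chance that some pair of arms differs by more than 0.5 SD in mean baseline VAS is about 33% with 16 per arm and 25% with 20, if arms are equal in size. Random arm sizes under simple randomisation raise these by one to two points. Given a baseline difference D, in units of the pre SD, the change-score difference shifts by (rho·k − 1)·D. At k = 1, rho 0.5 and D = 0.5 SD, that is (0.5 − 1) × 0.5 = −0.25 SD.

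**The case against.** The strongest reply is that nothing in the plan is wrong. The two-factor ANOVA suits the design and holds its type I error, and if 48 was calculated for the interaction test, that test has its stated power. This is correct, and the point is one of efficiency only.

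The gain also rests on quantities the documents do not give. If the intervention helps some women and not others, the post SD may exceed the pre SD. At k = 1.2 with rho 0.7 to 0.9, or k = 1.4 with rho 0.5 to 0.7, the gain is then nil or nearly so, and in one cell there is a loss of about 1 point. This stands, and it is why the range is shown. It does not make the planned test the better choice: the possible loss is trivial and most of the grid shows a gain.

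Two narrower objections are fair. The change score over-corrects only when rho·k is below 1; in two of the 16 cells (rho 0.9 with k = 1.2 or 1.4) it under-corrects. And chance imbalance averages to zero over randomisations and is already contained in the power figures, so step 7 explains the loss of efficiency and is not a further harm or a bias.

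Finally, the equivalence concerns the interaction term, which the plan does not name. It is the only sensible treatment test in that model. If the group main effect were used instead, simulated power with equal SDs would fall to 52%, 35% and 21% at rho 0.3, 0.5 and 0.7. That strengthens the case for naming the test.

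**Conclusion.** The concern holds. The planned analysis is valid but usually gives away precision that the trial has already paid for. Starting from 80% power at 48 women, ANCOVA changes power by between +18 and about −1 points over the assumed grid. With equal pre and post SDs, the gain is 14, 10, 6 and 1 points at rho 0.3, 0.5, 0.7 and 0.9. These sizes depend on the assumed correlation and SD ratio, and on the stated 80% referring to the interaction test. The direction in large samples depends on neither. The change should be made, but the trial's conclusions would not be invalid without it.

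**What to change.** In Statistical analysis of data, replace the sentence on the factorial ANOVA with wording such as:

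> The primary analysis will be an analysis of covariance of post-intervention VAS with arm (three levels) as factor and baseline VAS as covariate. The treatment test is the arm effect (2 df, alpha 0.05). Adjusted between-arm differences will be reported with 95% confidence intervals. Each questionnaire score will be analysed with the same model and its own baseline.

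A linear mixed model with the baseline means constrained to be equal across arms is an acceptable equivalent. The sample-size section should also state the effect size, the correlation and the test behind the 48.

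The cost is one reworded paragraph and one degree of freedom (44 error df instead of 45 at N = 48). No new data are needed, because pre-intervention measurements are already in the Work calendar.

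### The intended result on VAS is a fall over time with no reference to the control arm, and the positive result that releases the material is never defined

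*Combined protocol and SAP*

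**What the plan says.** The main objective is comparative: "The main objective of this study is to compare the effects of implementing a therapeutic educational program on pelvic floor pain and dysfunction" (Study Objectives). The design is randomised, with two programme arms and a control arm that is untreated until the post measurements are complete. Interventions/procedures to be performed describes the control arm's purpose as follows: "this group will serve to establish how the condition is maintained without a therapeutic approach".

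The analysis is set out under Statistical analysis of data: "a factorial ANOVA will be carried out, a repeated measurement factor (time) and a factor between groups (intervention". No effect in that model (time, group, or time by group) is singled out as the one that decides. The section then turns to results, which it frames as hoped-for changes. On pain it asks for "a significant reduction in the values of the VAS scale that corresponds to an improvement in terms of pain intensity". For the questionnaires it asks for significant changes in score that point to clinical improvement. Neither statement names a comparator.

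Under Ethical aspects and data confidentiality, the consequence is stated: "if the result is positive, the medical staff will be provided with the material with which the research has been carried out". Nothing in the protocol says what makes the result positive.

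**The concern.** A reduction in VAS values, in a design described as pre and post measurements, is a change over time. Women join because they have pain, and they rate that pain themselves, so some improvement on re-rating is plausible without any programme. The control arm is there to show how much. The stated target does not use it, and because no ANOVA effect is named as decisive, nothing else in the plan requires its use.

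A report could therefore follow this protocol, present a significant time effect or a significant fall in a programme arm, and call the result positive although the control arm fell as much. The material would then enter daily practice on evidence that does not separate the programme from waiting.

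**Working it through.** **Inputs from the documents.** Three groups, two measurement times, alpha 0.05 (sidedness not stated; two-sided assumed), 16 per group before and 20 per group after the drop-out allowance.

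**Assumed inputs.** The programme has no effect. All three arms share a true fall of d, in SD units of the change score. The documents give no figure for d, so a range is shown.

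**The plan's own figure.** Sample size calculation and sampling procedure says "An a priori size calculation was performed with an effect power of 80% and an alpha error of 0.05", and that "the sample must have a minimum of 48 participants, and that each group must have a minimum of 16". The step to 60 follows from an implied 20% drop-out: 48 / (1 − 0.20) = 60. The 48 cannot be confirmed or refuted, because the effect size, the pre/post correlation and the ANOVA effect are not given. Working backwards, 80% power at 48 needs f = 0.27, 0.23 or 0.18 for the time-by-group effect at correlations of 0.3, 0.5 and 0.7, or f = 0.24, 0.21 or 0.16 for the time effect. The sample size therefore does not show which effect was meant to decide.

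**Step 1: a significant fall in one arm.** For a paired t-test, the non-centrality is d√n with n − 1 degrees of freedom. With n = 20 and d = 0.5 it is 0.5 × √20 = 2.236, and the chance of a significant fall is p = 56.4%. The control arm has the same chance.

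**Step 2: at least one of the two programme arms.** The arms are independent, so the chance is 1 − (1 − p)². At d = 0.5 this is 1 − 0.436² = 81.0%.

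**Step 3: the time main effect of the planned ANOVA.** The non-centrality is N·d² on 1 and N − 3 degrees of freedom. With N = 60 and d = 0.5 it is 60 × 0.25 = 15, and the chance of significance is 96.8%.

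| Common fall d | One arm of 20 | Either of two arms of 20 | Either of two arms of 16 | Time effect, N = 60 |
|---|---|---|---|---|
| 0 | 2.5% | 4.9% | 4.9% | 5.0% |
| 0.2 | 13.3% | 24.9% | 21.3% | 33.1% |
| 0.3 | 24.6% | 43.2% | 36.3% | 62.7% |
| 0.5 | 56.4% | 81.0% | 71.4% | 96.8% |
| 0.8 | 92.4% | 99.4% | 97.7% | about 100% |

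The paired-test columns count falls only. The time-effect column is the two-sided F-test.

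**Step 4: the time-by-group effect.** A fall common to all arms cancels. In 40,000 simulated trials with d = 0.5 and 20 per arm, the interaction test was significant in 5.0%.

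**Step 5: sensitivity to the unit.** The SD of change equals the SD of VAS times √(2(1 − ρ)), so the two units coincide at ρ = 0.5. A fall of 0.5 SD of VAS at ρ = 0.3 is d = 0.5 / √1.4 = 0.42, giving 43% for one arm of 20 and 68% for either. At ρ = 0.7 it is d = 0.5 / √0.6 = 0.65, giving 78% and 95%.

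**The case against.** The strongest reply is that the sentence about VAS is read out of context. It describes hoped-for changes, not a decision rule. It comes just after an ANOVA with a between-groups factor, in a randomised trial whose objective is to compare. On that reading the reduction is judged within the comparison, the time-by-group test holds 5%, and the percentages for within-arm falls describe a paired test that nobody planned.

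Much of this stands. A reader might infer that the protocol lays down a formal before-after success criterion, or that it provides no between-group analysis. The documents support neither inference. Linking the VAS sentence to the word positive is also an inference, since that word is undefined. The reply does not supply the missing commitment, however: the time effect belongs to the planned ANOVA just as the interaction does, and nothing says which one carries the conclusion.

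The untreated fall is also unknown. Entry requires more than three months of dyspareunia but no minimum VAS, so no score threshold forces regression to the mean. With no fall the rates are at or below 5%. This limits how firmly the size can be stated.

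A reader might further infer that success in one modality would wrongly release both. That has little force: the two arms receive the same content, and what is released is the material.

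Finally, the heading of the analysis section is broken in the extracted text. The surviving fragment looks like the significance level. If lost words named a deciding effect, only the definition of positive would remain open.

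**Conclusion.** The point holds as a gap between the comparative design and the stated target. The plan contains an analysis that could answer the comparative question, but ties neither its intended result nor the word positive to it. As written, it permits a claim of success on a fall that the untreated arm shares.

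The size depends on the untreated fall. With no programme effect, the either-arm chance at 20 per arm runs from about 5% with no fall to 81% at 0.5 SD of change, against 5% for the time-by-group test throughout. These are the error rates of a reading that the text allows, not of a test that it prescribes. They assume a two-sided 5% level and the same fall in every arm.

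**What to change.** - **Target for VAS.** State it as a greater reduction than in the control group. Test it by the time-by-group effect and by a contrast of each programme arm with control, adjusted for baseline VAS and reported with a 95% confidence interval. The contrasts are needed because a three-group interaction does not show which arm differs from control, or in which direction. Comparing post-intervention VAS alone would not do: it discards the collected baseline and, under simple randomisation with about 20 per arm, leaves chance imbalance in the result.
- **Multiplicity.** State whether the two contrasts are adjusted. Unadjusted at two-sided 0.05, with 20 per arm and no programme effect, the chance that at least one favours a programme arm is about 4.6% by simulation, or 9% counting both directions.
- **Questionnaires.** Use the same between-group wording.
- **Release.** Under Ethical aspects and data confidentiality, define positive by the VAS contrast with control.
- **Optional.** State a minimum important VAS difference in advance and read the confidence interval against it.

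The cost is protocol wording, with no new data. The downside is that a positive result becomes harder to declare.
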